## 6.0 ADVERSE EVENTS (AE) AND STUDY MONITORING

### **Adverse Event Collection Requirements**

The following AEs will be recorded on data collection forms:

- All AEs that are attributed to doxycycline in the opinion of the site investigator
- All AEs meeting SAE definition

### Serious Adverse Events (SAEs)

An SAE is defined as any untoward medical occurrence that:

- Results in death
- Is life-threatening
- Requires inpatient hospitalization or prolongation of existing hospitalization
- Results in persistent or significant disability/incapacity
- Is a congenital anomaly/birth defect
- Is an important medical event that may not be immediately life-threatening or result in death or hospitalization but may jeopardize the patient or may require intervention to prevent one of the other outcomes listed in the definition above

All AEs that are recorded must have their severity graded. To grade AEs, sites should refer to the most recent version of Division of AIDS Table for Grading the Severity of Adult and Pediatric Adverse Events (DAIDS AE Grading Table).

## **Study Monitoring**

### *Study Team Monitoring*

The study team will monitor the conduct of the study through monthly summary reports of arms of accrual, and baseline characteristics and quarterly reports of data pooled over treatment arms of data completeness, specimen collection, and AEs. The study team will review individual participant-level safety data frequently to assess the relation of all reported AEs to study treatment. On a monthly basis, the study team will review by-arm summaries of premature study discontinuations and premature study treatment discontinuations (and reasons) and AEs.

### *DSMB*

An independent data safety and monitoring board (DSMB) will be convened for this study with expertise, from US and Kenya, in STIs, PrEP, and antimicrobial resistance and a biostatistician. The purpose of the DSMB is to monitor the study for operational futility, social harms, and efficacy. The DSMB will evaluate the progress of the project, including periodic assessments of accrual, retention, safety, performance and variation of the project sites, and other factors that can affect project implementation. The DSMB will review the study after approximately 1/3 and 2/3 of follow-up time with pre-specified stopping rules for efficacy and futility in terms of the efficacy of dPEP in reducing the incidence of gonorrhea, chlamydia, and syphilis overall, and the ability of the study to meet its objectives. The DSMB will be charged with the decision to recommend stopping the study early if interim analyses demonstrate emergent differences between the trial arms meeting pre-defined levels of significance, significant change in rate of doxycycline-resistant STIs, or significant safety concerns. At a minimum, a DSMB meeting must have a quorum of the chair and 2 other members. One or more Formal Interim Analysis meetings will be held to review data relating to relative effects of treatment on the trial outcomes. Patient safety and quality of trial conduct will also be reviewed at these meetings. The study team will carefully document any participants who become excluded from intervention arm due to pregnancy or are breastfeeding for careful review by DSMB for any adverse events to pregnant women or infants. Discussion of formal interim monitoring guidelines will be discussed at the Organizational Meeting prior to trial initiation. The DSMB will also consider factors external to the project when relevant information becomes available, such as policy changes or scientific developments that may have an impact on project implementation, safety, and integration of dPEP in the STI and HIV care clinics.

The DSMB will conduct reviews every six month and convene by teleconference. Open reports containing accrual and retention rates, participant characteristics, serious adverse events, and social harms, will be sent to the protocol team and DSMB members the week prior to the DSMB meeting. Only the DSMB members and the unblinded biostatistician will receive password-protected closed reports of STI endpoints by randomization arm. The DSMB membership will be restricted to individuals free of apparent significant conflicts of interest. The source of these conflicts may be financial, scientific or regulatory in nature. Reports from all reviews will be provided for submission to overseeing IRBs/ECs.

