### *Randomization :*

Participants will be randomized 1:1 to dPEP versus standard of care; randomization will be done in variable-sized blocks and using a computer based randomization system, following consent and eligibility confirmation.

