### **Pregnancy, breastfeeding, and HIV seroconversion**

#### *Management of dPEP with contraceptives and pregnancy:*

Contraception will be offered on-site but will not be required for study participation. The effectiveness of contraceptives or dPEP will not change with concomitant use. Women will be counseled on current Kenyan guidelines, which do not recommend use of doxycycline in pregnant women and participants

will stop dPEP should pregnancy occur. Women, who are not using LARC, will be screened for possible pregnancy at each quarterly visit using the WHO pregnancy checklist and if needed a urine pregnancy test will be conducted. Women will be counseled on current Kenyan guidelines, which do not recommend use of doxycycline in pregnant women and participants will stop dPEP should pregnancy occur; women can resume dPEP when no longer pregnant or breastfeeding. Pregnancies will be followed to completion. Any babies born to participants during the trial period will be passively followed for 1 year following their birth. Participants who deliver a baby during the trial will be asked to return for scheduled, quarterly study visits for a total of up to 12 months even though dPEP will be stopped if they are in the dPEP group. Additionally, they will be asked about the health of their baby at each study visit with continuation of questionnaire on health of their infant for first 12 months of infant's life. Breastfeeding will be an exclusion criterion for the trial, to limit exposure prior to demonstration of effectiveness; doxycycline is generally felt to be safe at standard doses in lactating women, although no formal declaration of safety exists for this population. Doxycycline is well-tolerated and recent data emphasize a strong safety profile when used by women, including in early pregnancy. Early data on safety of tetracycline found potential adverse effects when used in late pregnancy (specifically, bone and tooth effects), and cautions were extended to the entire tetracycline class, including doxycycline, despite lack of drug-specific data. Expert opinion is now calling for reconsideration of doxycycline use in pregnancy given significant differences between doxycycline and tetracycline and lack of evidence showing adverse events with doxycycline exposure in pregnant women.

*Management of PrEP with contraceptives and pregnancy:*

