### Statistical power and analysis

We propose a standard randomized superiority design, comparing dPEP to standard of care. The primary trial outcome will be the combined incidence of incident *C. trachomatis*, *N. gonorrhoeae*, and syphilis, compared between the randomization arms, to mirror the IPERGAY approach; analyses will also test each pathogen alone. We have been conservative in planning: first, we have planned for an STI incidence of 22% per year in the standard of care arm, which is less than the *C. trachomatis* incidence seen in our recent studies (**Table 3**) and second, we will calculate based on time to first incident STI alone, although we anticipate that some women will have repeat STIs contributing additional events and additional statistical power. We have planned for a 50% effect, comparable to the IPERGAY results and sufficiently great for public health benefit, but we anticipate that the *C. trachomatis* effect could be >50%, given universal susceptibility to doxycycline and

IPERGAY findings. With 80% power, 10% loss-to-follow-up, incidence of 22% vs. 11% (n=44 vs. 22 cases), and a two-sided alpha of 0.05, a sample size of n=550 is needed (n=275 per arm).

*Primary Analysis:*

We will analyze the composite endpoint of any of the three STIs as well as for *C. trachomatis* alone, and we will continue until there are sufficient *C. trachomatis* events (n=66) given the high incidence of this pathogen and its importance for reproductive morbidity (the consequence of which will be that the total number of events in the composite of *C. trachomatis*, *N. gonorrhoeae*, and syphilis will be greater than n=66). Analyses will be intention-to-treat, including women whether or not they continue dPEP (as well as whether or not they continue PrEP). STI incidence will be compared between arms using repeated measures analysis of proportions (e.g., generalized estimating equations [GEE]), given possibility of repeat infection within individuals. Per-protocol and adjusted analyses will be done as needed, controlling for potential confounders: demographics (e.g., age, education), sexual behavior (e.g., condom use, # partnerships), and beliefs (e.g., risk perception, dPEP/PrEP efficacy). SAS or R will be used.

*Secondary Analyses:*

Safety: Safety outcomes (i.e., AEs, tolerability, pregnancy, behavior) will be compared between arms using repeated measures analyses.

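### The dedicated DSMB review of pregnancy and infant adverse events names only women excluded from the intervention arm, and the SAP has no by-arm table of pregnancies and outcomes

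*Protocol*

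**What the plan says.** The protocol's DSMB section (6.0, Adverse Events and Study Monitoring) asks the study team to "document any participants who become excluded from intervention arm due to pregnancy or are breastfeeding for careful review by DSMB", so that adverse events in pregnant women or infants can be examined. No other sentence in either document names pregnancy or infant outcomes as material for the DSMB.

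Follow-up is wider. The section on contraceptives and pregnancy says: "Pregnancies will be followed to completion. Any babies born to participants during the trial period will be passively followed for 1 year following their birth". Women who deliver stay on quarterly visits "even though dPEP will be stopped if they are in the dPEP group". That condition makes sense only if control-arm women are followed too.

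On analysis, protocol section 10.0 states: "Safety outcomes (i.e., AEs, tolerability, pregnancy, behavior) will be compared between arms using repeated measures analyses". The SAP has no pregnancy-outcome endpoint in 2.2.3 and no pregnancy table in section 8. In section 8 pregnancy appears only as a reason for stopping dPEP (8.1.3). In 7.5.2 it is used to censor follow-up time in both arms.

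Beyond serious adverse events, the protocol records "All AEs that are attributed to doxycycline in the opinion of the site investigator". SAP 3.5 and 8.1.1 are likewise limited to doxycycline-related events. Serious adverse events are collected in both arms whatever their cause (SAP 3.5), tabulated by arm (SAP 8.1.2) and included in the DSMB open reports (protocol, DSMB). The by-arm closed reports are described there as covering STI endpoints.

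**The concern.** Pregnancy loss and infant illness occur without doxycycline. A series of dPEP-arm pregnancies alone cannot show whether the number of such events is higher than it would otherwise have been. Because dPEP is stopped once pregnancy occurs, any exposure falls mainly before the pregnancy is recognised. Early loss is then the outcome that most needs a comparator, and it is also one that the serious-event definition does not name.

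Safety is a primary objective, and the DSMB may recommend stopping over safety. Without control-arm counts it could read background losses as a signal, or be falsely reassured. The protocol accepts this logic elsewhere: under General symptom assessment it asks control women about symptoms precisely to obtain a comparator.

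**Working it through.** The plan states no expected number of pregnancies, so there is no figure to reproduce. The check has two parts: where each kind of event goes, and how many pregnancies are involved.

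**1. Routes named in the documents**

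| Event | dPEP arm | Control arm |
|---|---|---|
| Pregnancy, as a count | Documented for the DSMB when it leads to exclusion from dPEP | Followed; no DSMB route named |
| Maternal or infant event reported as serious | Serious-event reporting, plus the dedicated review | Serious-event reporting |
| Outcome not reported as serious | Dedicated review; also an AE if attributed to doxycycline | Followed; no DSMB route named |

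The arms differ in the first and third rows. An example from the third is a loss managed without admission and not judged an important medical event.

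**2. Share of pregnancies outside the dedicated review**

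Input: "Participants will be randomized 1:1 to dPEP versus standard of care". With RR the ratio of pregnancy rates (dPEP/control), the control share is 1/(1+RR).

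- RR = 1: 1/2 = 50%
- RR = 0.8: 1/1.8 = 56%
- RR = 1.25: 1/2.25 = 44%

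The protocol states that doxycycline does not reduce contraceptive effectiveness, which supports RR near 1. A change in behaviour in an open-label trial could move it.

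**3. Absolute numbers (illustration only)**

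Inputs: 223 per arm (SAP 3.3.1) or 275 per arm (protocol section 10.0); 10% loss to follow-up (both). Assumptions: loss spread evenly over the year, giving 1 − 0.10/2 = 0.95 person-years per woman, and pregnancy rates of 5, 10 and 20 per 100 person-years.

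- 223 × 0.95 × 0.05, 0.10, 0.20 = 10.6, 21.2, 42.4, or about 11, 21 and 42 per arm
- 275 × 0.95 × 0.05, 0.10, 0.20 = 13.1, 26.1, 52.3, or about 13, 26 and 52 per arm

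**4. What one arm can show**

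If none of m dPEP-arm pregnancies has a given adverse outcome, the exact 97.5% upper limit is 1 − 0.025^(1/m). For m = 11, 21 and 42 this is 28.5%, 16.1% and 8.4%. Nothing concurrent is available against which to read those limits.

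**5. What a second arm would add**

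Assume a 15% loss risk in both arms (not in the documents). The half-width of a 95% interval for the risk difference is about 1.96 × √(2 × 0.15 × 0.85 / m). For m = 11 it is 1.96 × 0.152 = 30 percentage points; for m = 42 it is 1.96 × 0.078 = 15 points. The normal approximation is rough at the smaller size. The comparison would be coarse, but it would exist.

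**The case against.** A reader might infer that control-arm pregnancies are absent from the DSMB's harm review altogether, and that the only background rate is lost. The documents do not support that. The DSMB sentence adds a listing and does not restrict other safety review. Serious adverse events from both arms reach the DSMB, and their definition covers death, hospitalisation, congenital anomaly and important medical events. What goes unused is the concurrent comparison within the trial, which is not the only conceivable background rate.

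Other points stand in part:

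- Reviewing exposed pregnancies case by case is a legitimate way to detect a signal, and the listing should stay.
- The important-medical-event criterion leaves room to report a loss managed without admission. Whether sites would do so is not stated, so unequal reporting of losses is possible but not shown.
- Read loosely, the breastfeeding half of the sentence could cover either arm. The pregnancy half cannot.
- Formal monitoring guidelines were left to an organisational meeting, and SAP 11.1 leaves the contents of data reports to a later version. Silence therefore does not prove that the DSMB never saw control-arm pregnancies.
- SAP section 10 places version 3.0 after the two-thirds interim review and version 4.0 near the end of data collection. Both formal interim reviews had probably passed, so the final-report table is the more useful part of the remedy.

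The small counts in steps 3 and 5 limit what any table can show. They do not favour a one-arm display over a two-arm one.

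**Conclusion.** The point holds in a limited form. The dedicated pregnancy and infant review is written for the intervention arm, no report named in either document gives pregnancies by arm as a denominator, and the comparison of pregnancy promised in the protocol has no counterpart in the SAP. Control-arm outcomes not reported as serious have no named route to the DSMB.

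About half of pregnancies lie outside the dedicated review. That rests on 1:1 allocation and equal pregnancy rates; the share is 44% to 56% for rate ratios of 1.25 to 0.8. The counts of 11 to 42 per arm rest on assumed pregnancy rates and cannot be derived from the documents. The primary efficacy result is unaffected. This is an inexpensive improvement to safety reporting that should be made.

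**What to change.** 1. Reword the sentence in the protocol's DSMB section so that every pregnancy, its outcome (including any loss), breastfeeding and infant health are documented in both arms. Show these by arm, with the number of pregnancies as denominator, in any remaining DSMB closed report.
2. Add the same descriptive table to SAP section 8 for the final report: pregnancies, outcomes and infant events by arm, with counts and a risk difference with 95% CI. Include a row for pregnancies whose outcome is unknown at data lock, because the final analysis follows the 12-month visits (SAP 4.2) and some pregnancies will run past them. Show the number randomised as well, because a denominator of pregnancies conditions on an event after randomisation.
3. Keep the listing of dPEP discontinuations for pregnancy as a separate one-arm item.

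The cost is one protocol sentence and one table. The follow-up already planned in both arms supplies the data, and no treatment rule changes. Counts will be small and intervals wide, so the table should be labelled descriptive, consistent with the SAP's decision not to test adverse events between arms.

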## **8.0 CLINICAL MANAGEMENT ISSUES**

### **Toxicity**

Only toxicities related to study medications provided through the study will be considered in the toxicity management section.

#### Grade 1 or 2

Participants who develop Grade 1 or 2 toxicity (per DAIDS toxicity table) felt to be related to doxycycline may continue study treatment at the discretion of the site investigator with close follow-up. If a participant chooses to discontinue study treatment, the site should notify the study protocol team within 7 days. These participants will remain on study, off study treatment and have all evaluations performed per current clinical guidelines.

#### Grade 3

- Participants who develop a Grade 3 toxicity thought by the site investigator to be related to study drug should have study drug held. The participant should be reevaluated weekly until the AE returns to Grade ≤2, at which time study drug may be reintroduced at the discretion of the site investigator in consultation with the protocol team.
- Participants experiencing Grade 3 toxicity requiring permanent discontinuation of study drug should be followed weekly until resolution of the toxicity. Participants will have premature study treatment discontinuation evaluations performed as noted in most up to date clinical evidence. These participants will remain on study, off study treatment and have all evaluations performed per current clinical guidelines.

#### Grade 4

- Participants who develop a Grade 4 symptomatic toxicity felt to be related to the study drug will have study drug permanently discontinued.
- Participants experiencing Grade 4 toxicity requiring permanent discontinuation of study drug should be followed weekly until resolution of the AE or return to baseline. These participants will remain on study, off study treatment and have all evaluations performed per current clinical guidelines.

### *Specific Management of Toxicities Related to Study-Provided Drugs*

#### Possible intracranial hypertension (IH)

Participants taking doxycycline who report new or worsening headaches, visual changes or vision loss should have doxycycline temporarily discontinued and evaluated for IH, including a fundoscopic exam to look for papilledema. If IH is ruled out or an alternate etiology identified, doxycycline may be restarted, at the discretion of the site investigator.

#### Skin erythema

Increased photosensitivity is a known possible side effect of doxycycline. Doxycycline should be discontinued if skin erythema develops and may be reinstated when resolved at the discretion of the site investigator. Any SAE should lead to permanent discontinuation of doxycycline.

#### Fixed drug eruption

Suspected fixed drug eruption should be evaluated for possible etiologies – if a doxycycline fixed drug eruption is suspected, doxycycline should be stopped.

#### Allergic reactions

Doxycycline should be discontinued permanently if an allergic reaction is suspected. These participants will remain on study, off study treatment and have all evaluations performed per current clinical guidelines.

## 9.0 CRITERIA FOR DISCONTINUATION

### Premature Study Treatment Discontinuation

- Requirement for prohibited concomitant medications or other contraindication to doxycycline
- Occurrence of an AE requiring discontinuation of doxycycline
- Request by participant to terminate study treatment
- Clinical reasons believed life threatening by the physician, even if not addressed in the toxicity section of the protocol
- Requirement for chronic tetracycline use (>14 days)
- Pregnancy
- Breastfeeding

Participants who stop dPEP should be continued on study, off dPEP with continued evaluations. The reason for doxycycline discontinuation should be recorded.

### Premature Study Discontinuation

- Request by the participant to withdraw
- Participant judged by the investigator to be at significant risk of failing to comply with the provisions of the protocol as to cause harm to self or seriously interfere with the validity of the study results
- At the discretion of the IRB/EC, funder, or Office for Human Research Protections (OHRP)

## 10.0 STATISTICAL CONSIDERATIONS

### Outcome measures

*Primary outcome:* Combined incidence of *N. gonorrhoeae*, *C. trachomatis*, or early syphilis infection by laboratory-based diagnosis (e.g., positive *N. gonorrhoeae* or *C. trachomatis* based on NAAT or syphilis based on four-fold increase in non-treponemal titers).

### Secondary outcomes:

- Safety: Safety assessment will be measured in both arms: serious adverse events (SAEs), related all AEs and discontinuations (in the dPEP arm only), and a standardized symptom assessment for doxycycline-specific side effects (e.g., nausea, pill esophagitis, photosensitivity, vaginal candidiasis).
- Acceptability: Longitudinal change in qualitative themes and associated barriers and facilitators
- Adherence: We will explore the self-reported measures and SMS data, defining adherence as the percentage of times that dPEP was taken following an episode of condomless intercourse. Stored vaginal swabs for Y chromosome testing can be available for later validation.
- Resistance: The detection of the plasmid-encoded *tet(M)* gene and/or *tetR* genetic resistance determinants is indicative of phenotypic resistance to tetracycline
- Cost: The incremental cost effectiveness ratio (ICER) per incident STI case averted and DALY averted

### Statistical power and analysis

We propose a standard randomized superiority design, comparing dPEP to standard of care. The primary trial outcome will be the combined incidence of incident *C. trachomatis*, *N. gonorrhoeae*, and syphilis, compared between the randomization arms, to mirror the IPERGAY approach; analyses will also test each pathogen alone. We have been conservative in planning: first, we have planned for an STI incidence of 22% per year in the standard of care arm, which is less than the *C. trachomatis* incidence seen in our recent studies (**Table 3**) and second, we will calculate based on time to first incident STI alone, although we anticipate that some women will have repeat STIs contributing additional events and additional statistical power. We have planned for a 50% effect, comparable to the IPERGAY results and sufficiently great for public health benefit, but we anticipate that the *C. trachomatis* effect could be >50%, given universal susceptibility to doxycycline and

IPERGAY findings. With 80% power, 10% loss-to-follow-up, incidence of 22% vs. 11% (n=44 vs. 22 cases), and a two-sided alpha of 0.05, a sample size of n=550 is needed (n=275 per arm).

*Primary Analysis:*

We will analyze the composite endpoint of any of the three STIs as well as for *C. trachomatis* alone, and we will continue until there are sufficient *C. trachomatis* events (n=66) given the high incidence of this pathogen and its importance for reproductive morbidity (the consequence of which will be that the total number of events in the composite of *C. trachomatis*, *N. gonorrhoeae*, and syphilis will be greater than n=66). Analyses will be intention-to-treat, including women whether or not they continue dPEP (as well as whether or not they continue PrEP). STI incidence will be compared between arms using repeated measures analysis of proportions (e.g., generalized estimating equations [GEE]), given possibility of repeat infection within individuals. Per-protocol and adjusted analyses will be done as needed, controlling for potential confounders: demographics (e.g., age, education), sexual behavior (e.g., condom use, # partnerships), and beliefs (e.g., risk perception, dPEP/PrEP efficacy). SAS or R will be used.

*Secondary Analyses:*

Safety: Safety outcomes (i.e., AEs, tolerability, pregnancy, behavior) will be compared between arms using repeated measures analyses.

Adherence: We will explore the self-reported measures and SMS data, defining adherence as the percentage of times that dPEP was taken following an episode of condomless intercourse. Stored vaginal swabs for Y chromosome testing can be available for later validation, as noted in Aim 1 above. For hair, we plan three analyses, focused on 1) describing overall adherence in the population, 2) understanding the relationship between adherence and STI protection, and 3) exploring for cross-over (contamination between arms) that could occur since doxycycline is available in the community. We will complete a descriptive analysis of nonadherence events (defined as self-report of unprotected sex in last 3 months corresponding with elevated pill count or undetectable hair drug level), both for dPEP (dPEP arm only) and for PrEP, with log binomial regression with GEE to account for repeat measures of adherence over time. Adjusted analyses will control for potential confounders as in Aim 1.

Acceptability: Quantitative analysis will be completed using GEE to test associations between facilitators/barriers and randomization arm, dPEP adherence, and STI outcomes. Data will be analyzed to understand factors impacting acceptability of dPEP, including demographics, stigma, fertility desire, dPEP effect on sexual and preventative decision making. Qualitative analysis will take a longitudinal approach. Interview discussions will be recorded, transcribed, and translated into English. Transcripts will be reviewed separately by two investigators for completeness and initial theme generation. We routinely use rapid debriefing reports to obtain real-time information; formal coding and analysis will be performed with Atlas.ti, using inductive approach informed by theoretical framework of acceptability (TFA), a recently developed approach to acceptability research of medical interventions. The components of TFA are affective attitude, burden, ethicality, intervention coherence, opportunity costs, perceived effectiveness, and self-efficacy. Initial code generation of the transcript themes will capture experiences and context of dPEP use. Codes will be reviewed for consistency and inter-coder agreement with consensus code generation by themes. Following a similar process, transcripts from Months 6 and 12 will be coded with reference to the baseline codes to capture temporality of experiences and contexts within each participant. Codes generated from transcripts at Months 6 and 12 will be compared across participants to establish differences and similarities across the sample. The code will reflect the longitudinal data and emergence of new codes. Descriptive thematic analyses will be done at baseline and over time.

Resistance: The impact of dPEP on *C. trachomatis* and *N. gonorrhoeae* resistance will be measured by comparing the overall rates of doxycycline-resistant events occurring in the dPEP arm to rates in the

control arm, at baseline and separately during follow-up adjusted for medical factors that confound the dPEP-resistance risk relationship.

**Cost:** Using the effectiveness estimated through Aim 1 and the costing and modeling from this study, the incremental cost effectiveness ratio (ICER) per incident STI case averted, and disability-adjusted life year (DALY) averted will be estimated for dPEP compared to the control arm. Sensitivity analyses will address adherence, risk compensation, and programmatic issues (e.g., medication stock-outs). The primary analysis will be from a programmatic perspective, the purview of decision makers. Following suggested update to cost effectiveness definition for low-income countries, interventions will be considered cost-effective if the ICER is 500 USD per DALY averted. In the budget impact analysis, we will consider direct program costs, and ensure that measurements of programmatic costs reflect the opportunity cost of the resources used in delivering services. We will report on all costs using a recommended discount rate of 3% per year, as well as an alternative 5% discount rate and undiscounted inputs. This will facilitate comparison to other strategies and help decision makers to define priorities and allocate resources.

